1.0 OBJECTIVES

1.1 Primary Objective

To develop a Spanish-language version of the ANCHOR HSIL HRQoL Index (HQI) using state-of-the-art measure development methodology that captures the most important HRQoL symptoms and concerns of those persons diagnosed with anal HSIL and either treated or untreated for anal HSIL.

Upon completion, the anal HSIL Symptom Index will be validated within the Anal Cancer/HSIL Outcomes Research Study (ANCHOR), a large randomized controlled trial. The ANCHOR protocol will be amended through the AMC and CTEP at that time.

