This study adds a seventh phase to the development paradigm conducted with protocol AMC-A02, which will use the translated aHRSI in Spanish to complete cognitive interviews of Spanish-speaking participants. We will be conducting cognitive interviews (see Appendices [VI](#) and [VII](#)) of the finalized measure in Spanish (see Appendices [XI](#) and [XII](#)) to establish the content validity of the measure in Spanish. In addition to the cognitive interviews, we will collect a brief demographic form, and collect information on the participants preferred language and language proficiency (see Appendices [IX](#), [X](#), [XIII](#), and [XIV](#)) for each participant. We will enroll up to 40 eligible HIV-positive participants from participating ANCHOR sites using the same eligibility criteria as AMC-A02 phase 2 (except the age limit is lowered to 18 and the added criteria that Spanish be their first language as per self-report) over three rounds of cognitive interviewing, as was done for the English language version in AMC-A02 phases 4-6.¹⁸

- Cognitive Interviews in Spanish (Round 1): The process for conducting the cognitive interviews will be the same as for the English ones outlined above in Phase 4. We will plan to consent 20 Spanish speaking participants in order to complete 20 cognitive interviews.
- Cognitive Interviews in Spanish (Round 2): We will complete Phase 5 in Spanish in the exact same method as we did for the English version if it is necessary. If necessary, we will recruit up to 10 participants for this Phase 5 round.
- Cognitive Interviews in Spanish (Round 3): We will complete Phase 6 in Spanish in the exact same method as we did for the English version if it is necessary. If necessary, we will recruit up to 10 participants for this Phase 5 round.

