APPENDIX VII: COGNITIVE INTERVIEW SCRIPT – ENGLISH

Introduction (Read to Participant)

- *It is important to understand the experiences of people who are diagnosed with Anal HSIL (pre-cancer lesion in the anus) (and any treatments they receive – IF APPLICABLE). That is why we are asking for your help today. We would like you to answer some questions for the next hour. We will be asking you to use some of the new questions we are developing, and then to tell us your experiences answering these questions, such as how easy or difficult the questions were to answer. Some of these questions will ask you about your symptoms related to Anal HSIL (and treatment – IF APPLICABLE). Some questions will ask about how Anal HSIL (and treatment – IF APPLICABLE) has impacted parts of your everyday life. With your help, we will be able to have a better understanding of what people who have Anal HSIL are experiencing.*
- *The information that you provide today will be used for research purposes, and will help people in the future.*

ANCHOR ANAL HSIL HEALTH-RELATED QUALITY OF LIFE INDEX---DRAFT 2015v.7

Below is a list of statements that other people diagnosed with anal HSIL (pre-cancer lesion in the anus) and treated or actively monitored have said are important. Please check the box to select your answer based on your experiences in the past 7 days. If you have **ANY** trouble selecting a response for any statement or find something hard to understand, please check the box in the *Check if Difficult to Understand* column for that statement. Please let me know when you have completed each of the three sections (Physical Symptoms, Physical Impacts, Psychological Symptoms).

PHYSICAL SYMPTOMS		Check if Not Applicable	Not at all 0	A little bit 1	Somewhat 2	Quite a bit 3	Very much 4	Difficult To Understand
1. I have anal pain								
2. I have pain other than anal pain								
3. I have pain during bowel movements								
4. I have constipation								
5. I have bleeding from the anus								
6. I have itching in or around the anus								
7. I have discharge (wetness) in my anal area								
8. I have burning sensations in the anal area								
9. I have urgency for bowel movements								
PHYSICAL IMPACTS		Check if Not Applicable	Not at all 0	A little bit 1	Somewhat 2	Quite a bit 3	Very much 4	Difficult To Understand
10. I have problems with my physical ability to move around								
11. I have problems with sitting								

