For the following, you should find an item that the patient responded with a 2 and determine how that differed from a 1 or 3 response. Similarly, you should find an item that the patient responded with a 3 and determine how that differed from a 2 or 4 response.

You answered (2). How did you come up with that answer? What makes that a better answer than (x+1)? What makes (x) a better answer than (x-1)?

You answered (3). How did you come up with that answer? What makes that a better answer than (x+1)? What makes (x) a better answer than (x-1)?

Were there any other words in the answer choices that were confusing or hard to understand? If so, which ones?

Cognitive Interviewing Probes – Recall period

How easy or difficult was it to think about your experiences over the last 7 days? Is there a better time period for considering your experiences?

Summary Questions

Now that you have finished answering all the items, I would like to ask you a few final questions about the survey as a whole. Remember that we are only interested in improving our survey, so if something was confusing or hard to answer then make sure you tell us that, because that is exactly what we want to find out today.

- *Did you find this interview difficult?*
- *Was the survey too long?*
- *Does any one survey statement stick out in your mind as being particularly difficult for you?*
- *Is there anything else you would like us to know about this questionnaire? Do you have any suggestions for improving it for others?*

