APPENDIX VIII: COGNITIVE INTERVIEW SCRIPT – SPANISH

Introducción (léale al participante)

Es importante entender las experiencias de las personas diagnosticadas con HSIL anal (lesiones precancerosas en el ano) (y cualquier tratamiento que reciban – SI APLICA). Por eso le estamos pidiendo ayuda hoy. Nos gustaría que conteste algunas preguntas durante la próxima hora. Le pediremos que conteste algunas de las preguntas nuevas que estamos desarrollando y que luego nos cuente sus experiencias contestando estas preguntas, como por ejemplo, qué tan fácil o difícil fue contestarlas. Algunas preguntas tendrán que ver con los síntomas relacionados con HSIL anal (y tratamiento – SI APLICA). Otras tendrán que ver con la manera en que HSIL anal (y tratamiento – SI APLICA) ha impactado aspectos de su vida diaria. Usted nos ayudará a entender mejor lo que experimentan las personas con HSIL anal. La información que nos de hoy se utilizará en investigación, y ayudará a otras personas en el futuro.

ÍNDICE DE SÍNTOMAS RELACIONADOS CON LA SALUD ANCHOR

A continuación presentamos una lista de afirmaciones que otras personas diagnosticadas con HSIL (lesión precancerosa en el ano) y que han sido tratadas o monitoreadas activamente han dicho que son importantes. Por favor seleccione la casilla con su respuesta basándose en sus experiencias en **los últimos 7 días**.

Si tiene **ALGÚN** problema seleccionando una respuesta o le cuesta contestar algo, por favor seleccione la casilla en la columna que dice, *Difícil de entender*. Déjeme saber cuando haya terminado cada una de estas secciones (Síntomas físicos, Impactos físicos, Síntomas psicológicos).

SÍNTOMAS FÍSICOS	Escoja si no aplica	Para nada 0	Un poco 1	Algo 2	Bastante 3	Muchísimo 4	Difícil de entender
1. Tengo dolor anal							
2. Tengo dolor pero no en el área anal							
3. Tengo dolor cuando entro al baño a defecar							
4. Tengo estreñimiento							
5. Tengo sangrado del ano							
6. Tengo picazón en el ano o alrededor del ano							
7. Tengo una secreción (mojado) en el área anal							
8. Tengo sensación de ardor en el área anal							
9. Siento urgencia de entrar al baño a defecar							
IMPACTOS FÍSICOS	Escoja si no aplica	Para nada 0	Un poco 1	Algo 2	Bastante 3	Muchísimo 4	Difícil de entender
10. Tengo problemas con mi capacidad física para movilizarme							
11. Tengo problemas para sentarme							

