12. Tengo problemas terminando las tareas de la casa (por ej., limpiar, cocinar, hacer la colada, llevar la casa)							

13. Tengo problemas con mi arreglo personal diario (por ej., bañándome, vistiéndome, afeitándome)							
14. Tengo problemas participando en actividades de ocio (por ej., mirar televisión, relajarme)							
15. Tengo problemas participando en actividades sociales (por ej., salir a comer, visitar amigos)							
16. Tengo problemas siendo productivo en el trabajo							
SÍNTOMAS PSICOLÓGICOS	Escoja si no aplica	Para nada 0	Un poco 1	Algo 2	Bastante 3	Muchísimo 4	Difícil de entender
17. Tengo dificultad concentrándome							
18. Me ha disminuido el placer de la actividad sexual anal							
19. Me ha disminuido el placer de cualquier forma de actividad sexual diferente a la actividad sexual anal							
20. Me ha disminuido el deseo por la actividad sexual anal							
21. Me ha disminuido el deseo por formas de actividad sexual diferentes a la actividad sexual anal							
22. Me preocupa que mi enfermedad empeore							
23. Tengo ansiedad							
24. Tengo depresión							
25. Tengo problemas con mis relaciones íntimas							

Ahora nos va a contar cuáles fueron sus respuestas para cada una de las 25 preguntas (REGISTRE LAS RESPUESTAS EN SU FORMULARIO). Por favor cuénteme si escogió “Difícil de entender” o “No aplica”.

Sondeo de la entrevista cognitiva – General

Primero, para las cosas que contestó, fue fácil de contestar....

- Todo el tiempo
- La mayoría del tiempo
- Algunas veces
- Nunca

¿Hubo algún problema que hizo difícil contestar la encuesta en general? Si sí, ¿qué?

Ahora examinemos lo que le pareció difícil de entender. Olvidándose de las cosas que ya me ha contado, ¿cuáles fueron los problemas que surgieron en esos momentos?

(Algunos de los asuntos planteados durante esta porción podrían hacer resaltar problemas específicos que forman parte de nuestro objetivo. Por favor tome nota de ellos para que no vuelvan a surgir durante la entrevista).

Sondeo de la entrevista cognitiva – Instrucciones

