Para lo siguiente debe encontrar un ítem para el que el paciente contestó con un 2 y determinar de qué manera difirió de una respuesta 1 o 3. También debe encontrar un ítem para el que el paciente contestó con un 3 y determinar de qué manera difirió de una respuesta 2 o 4.

Usted contestó (2). ¿Cómo llegó a esa respuesta? ¿Por qué es una mejor respuesta que (x+1)? ¿Por qué (x) es una mejor respuesta que (x-1)?

Usted contestó (3). ¿Cómo llegó a esa respuesta? ¿Por qué es una mejor respuesta que (x+1)? ¿Por qué (x) es una mejor respuesta que (x-1)?

¿Hubo algunas otras palabras en las opciones de respuesta que eran confusas o difíciles de entender? Si sí, ¿cuáles?

Sondeo de la entrevista cognitiva – Período recordatorio

¿Qué tan fácil o difícil fue pensar en sus experiencias en los últimos 7 días? ¿Existe un mejor período de tiempo para considerar sus experiencias?

Respuestas de resumen

Ahora que ha respondido todo, me gustaría hacerle un par de preguntas finales sobre la entrevista en su totalidad. Recuerde que tan solo nos interesa mejorar la encuesta, por lo que si algo le resultó confuso o difícil de contestar asegúrese de decirlo—eso es exactamente lo que queremos averiguar.

- *¿Le pareció difícil esta entrevista?*
- *¿Le pareció que la entrevista fue demasiado larga?*
- *¿Alguna afirmación en la encuesta sobresalió por ser particularmente difícil para usted?*
- *¿Hay algo más que le gustaría que supiéramos sobre este cuestionario? ¿Tiene alguna sugerencia para mejorarlo para otras personas?*

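### The Spanish interview script probes item 13 with a phrase the item does not contain and changes the difficulty-box instruction; both should be aligned with the measure

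*Protocol*

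**What the plan says.** The primary objective (Section 1.1) is a Spanish version that "captures the most important HRQoL symptoms and concerns of those persons diagnosed with anal HSIL". Sections 2.3 and 4.0 give the purpose of the interviews as "to establish the content validity of the measure in Spanish". The Synopsis limits the work to repeating AMC-A02 phases 4 to 6, the cognitive interviews. Section 2.3 says the second and third rounds will be done "in the exact same method as we did for the English version if it is necessary".

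In both scripts the participant completes the questionnaire and marks a box beside any troublesome item. The English instruction (Appendix VII) covers "trouble selecting a response for any statement or find something hard to understand". The Spanish one (Appendix VIII) covers "problema seleccionando una respuesta o le cuesta contestar algo". The column is headed *Difícil de entender*.

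The participant then reads back every answer: "Ahora nos va a contar cuáles fueron sus respuestas para cada una de las 25 preguntas". Marked items are discussed, question-specific probes follow, and the interview ends with open questions such as "Is there anything else you would like us to know about this questionnaire" and, in Spanish, "Tiene alguna sugerencia para mejorarlo para otras personas".

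**The concern.** A meaning probe is evidence about an item only if it uses the item's words. When the interviewer asks what a phrase means as used in a statement, and the statement uses another phrase, the answer concerns wording that the measure does not contain. Item 13 is where this matters most. Its Spanish text is a non-literal rendering of the English idea of taking care of oneself, so it is one of the items whose translation most needs checking.

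The instruction matters because the difficulty box is the main route by which an item without its own probe comes up for discussion. A participant can find an item easy to answer without having understood it as intended. An instruction about answering steers such a participant away from the box.

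Lost evidence is hard to recover. Recordings are destroyed within 48 business hours and no transcripts are made (Section 3.4.2). Later rounds cannot be counted on either. Section 2.3 makes rounds 2 and 3 conditional, while the Synopsis attaches a condition only to round 3. The minimum enrolment of 20 in Section 3.3.1 fits the former reading. The documents leave the status of round 2 unclear.

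**Working it through.** The plan gives no figure to reproduce; Section 5.0 states that no formal statistical analysis plan is needed. The check is a comparison of texts and a count.

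**Step 1. Wording, side by side (Appendix VIII unless stated).**

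| Place | Measure or English text | Spanish probe or instruction | Effect |
|---|---|---|---|
| Item 13 | *arreglo personal diario* (also Appendix XII) | *problemas personales diarios* | Drops *arreglo*; a different phrase is tested. The three examples are kept |
| Difficulty box | English: hard to understand | Spanish: hard to answer | Shifts from comprehension to answering; the column title keeps comprehension |
| Item 12 | *tareas de la casa*; last example is *llevar la casa* in the script, *administrar la casa* in Appendix XII | Probe adds *diarias* | Small, but script, probe and measure do not agree |
| Item 3 | *cuando entro al baño a defecar* | *durante la defecación* | Meaning kept |
| Item 16 | *siendo productivo* | *productividad* | Meaning kept |
| Item 22 | *me preocupa* | *estoy preocupado* | Meaning kept |
| Top of response scale | *muchísimo* | *mucho* | Weaker word than the printed option |

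The English item 13 and its probe agree, so that mismatch arose in the Spanish script. Purely grammatical changes, such as a change of person, are left out of the table.

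**Step 2. Items with an item-specific probe.** Each of the 25 items was matched to the question-specific probes; the result is the same in both languages.

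- With a probe: 1-3 (one shared pain question), 6, 7 (only if discharge is experienced), 8, 10-22 and 25. That is 3 + 1 + 1 + 1 + 13 + 1 = 20.
- Without: 4 (constipation), 5 (bleeding), 9 (bowel urgency), 23 (anxiety) and 24 (depression). 25 - 20 = 5, and 5/25 = 20%.
- By section: 3 of 9 physical symptoms, 0 of 7 physical impacts, 2 of 9 psychological symptoms.

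The count depends on the definition. If every item had to have its own question on meaning, items 1, 2 and 3 (shared question on whether the pains are separate), 7 (word preference) and 19 and 21 (asked only how they differ from another item) would also lack one: 5 + 6 = 11, and 11/25 = 44%.

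**Step 3. Coverage.** Neither script asks directly whether a symptom or concern has been left out. The closing questions are open but concern the questionnaire in general.

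**Step 4. Time for added questions.** One coverage question plus five meaning probes is 6. At an assumed 30 to 60 seconds each, 6 × 30 s = 3 min and 6 × 60 s = 6 min. Against the 45-60 minute session in the Synopsis, that is between 3/60 = 5% and 6/45 = 13%.

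**The case against.** The strongest reply is that this study tests a translation of a measure whose content was settled earlier. Section 2.3 describes expert consultation, independent elicitation of symptoms and concerns from HIV-positive participants, and drafting from both, all before the phases repeated here. Leaving out a coverage question is then a matter of scope. The protocol also says that the Spanish process follows the English one, and the script speaks of specific issues being targeted, so selective probing looks deliberate. No passage requires a probe for each item, and four of the five unprobed items are short, plain statements.

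That reply stands against any claim that the missing probes or coverage question are errors. Its one gap is that the protocol does not say the earlier elicitation included Spanish speakers with limited English, so a coverage question could still add something.

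On item 13, the probe keeps the examples and points back to the statement, and participants are asked to have the questionnaire with them (Appendix VI). This limits the harm but does not remove the mismatch.

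A reader might infer that the interviews cannot establish content validity in Spanish, or that a fifth of the measure goes untested. The documents do not support this. The difficulty column, its follow-up and the read-back apply to all 25 items. The response-scale probe may also reach an unprobed item, and Section 7.1 describes the interviews as semi-structured.

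**Conclusion.** The point holds as a set of wording errors in Appendix VIII. One is material (the item 13 probe), one affects how problems are flagged (the difficulty-box instruction), and the rest are small (items 3, 12, 16 and 22 and the scale probe). Followed as written, the script would collect comprehension evidence on a phrase absent from the measure. It would also give a weaker prompt to flag misunderstanding than the English script does.

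The five unprobed items and the absent coverage question are opportunities for improvement shared with the English script. The figure of 5 in 25 rests on the lenient definition in Step 2. Existing safeguards give partial cover, but an item misread with confidence may raise no mark. This is worth correcting, but it does not undermine the study.

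**What to change.** Corrections to Appendix VIII, none of which adds interview time:

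- Reword the item 13 probe so that it quotes *arreglo personal diario*.
- Make the difficulty-box instruction refer to things hard to understand, as the English does.
- Align the wording for items 3, 12, 16 and 22 and the top response option across the script, its probes and Appendix XII, including the last example in item 12.

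Optional additions to Appendices VII and VIII:

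- One question asking whether any symptom or concern from anal HSIL, its treatment or its monitoring was not asked about.
- The script's standard meaning probe for items 4, 5, 9, 23 and 24, with item 9 first because its Spanish text is the most reworded of the five.

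The additions would take about 3 to 6 minutes under the assumption above. They should be timed first, since the protocol shows no slack in the 45-60 minute session and participants are told to expect an hour. Any of these changes needs a written amendment approved by the Protocol Chair and by the IRB of each participating institution (Section 7.2), so they are best made together. No extra participants or staff are needed. If time is tight, the corrections can go ahead without the additions.

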3.0 PARTICIPANT SELECTION

Participants who have been diagnosed with HSIL within the prior nine months will be recruited for all phases of this protocol. The target population is volunteers who meet all the inclusion/exclusion criteria, and who are presumed eligible for the ANCHOR study. Recruiting sites will be responsible for referring participants into the HRQoL Index study who meet the eligibility criteria listed below.

3.1 Eligibility Criteria

- 3.1.1 HIV-1 infection
- 3.1.2 Age 18 years or older. This age restriction is intended to enrich the study population at risk for cancer since anal cancer occurs only rarely under this age even among HIV-infected individuals. Less than 1% of anal cancers occur under the age of 35 years¹⁵.
- 3.1.3 Biopsy-proven anal HSIL within the prior nine months
- 3.1.4 Participant must have received anal HSIL treatment in the last nine months. If the participant's treatment plan is "observation," the participant must have been diagnosed with anal HSIL in the last nine months.
- 3.1.5 Life expectancy of greater than 5 years
- 3.1.6 Fluent in Spanish with limited English proficiency, per self-report

3.2 Exclusion Criteria

Participants who do not fulfill the criteria as listed in Section 3.1 above, are ineligible. Additionally, the presence of any of the following conditions will exclude a participant from study enrollment:

- 3.2.1 History of anal cancer
- 3.2.2 Inability to understand a written consent form

3.3 Number of Participants to be Enrolled

3.3.1 Proposed sample size

This study will enroll a minimum of 20 participants and a maximum of 40 participants.

3.3.2 Accrual rate

Approximately 5 participants per month.

3.4 Participant Referral and Enrollment Procedures

This study will be recruiting from any sites participating in AMC-A01 as long as this protocol is determined to be exempt by the local IRB. Each recruitment site PI has agreed to participate and will identify and refer eligible patients. Upon MSKCC IRB approval, the exempt protocol will be provided to the PI at each recruitment site for review by their IRB. Once each site's IRB approval is obtained, each site will be provided with instructions on the referral process and a list of site-specific unique identification numbers that will be used for each patient referral. Referring sites will not collect any data; they will only be

responsible for assuring eligibility of all patient referrals. After confirming a patient's eligibility, the site physician or designee will provide an Information Sheet about the study containing the MSK RSA contact information, financial and transportation compensation information, and the unique identification number. The Information Sheet will have a gray box on the top stating "This box for Clinician Use Only. Clinician, please circle appropriate letter." The appropriately circled letters will create the unique identification number. It will be up to the patient to initiate a call to the MSK RSA, although one or more sites may provide telephone access within their clinics for referred patients to call the MSKCC contact. The unique identification number will have encoded information regarding from which site the patient has been referred, which of four treatment modalities the patient used, and the volume of disease. The encoding will not be interpretable by anyone except the referring site and the MSKCC study staff. For example, Laser Surgery Center will be given Information Sheets with referral numbers 100-199, Einstein Montefiore will be given Information Sheets with referral numbers 200-299 and 400-499 ([name] clinic), and Weill Cornell will be given Information Sheets with referral numbers 300-399. Treatment modality will then be indicated by circling the first letter of the correct treatment modality. For example, a participant who is being observed without treatment will be represented with a circled "O," Ablative with a circled "A," Topical with a circled "T," and Surgery with a circled "S." If the patient has undergone multiple treatment modalities, the referral staff will select the most recently received treatment. Next, disease volume will be indicated by circling either L or H. L will correspond with HSIL lesion size covering Less than or equal to 50% of the anal canal/perianal region and H will correspond with HSIL lesion size covering Higher than 50% of the anal canal/perianal region. An example code could then be 100-AL; this indicates the patient was referred from Laser Surgery Center, has received ablative treatment, and has HSIL lesion covering less than 50% of the anal canal/perianal region. It is important that the referral site indicate via the treatment code how each patient was treated, and the volume of disease, because patients may not accurately report treatment modality. The sampling strategy must be monitored by the MSKCC study staff in order to assure proper patient sampling.

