Hyfrecation/electrocautery is an ablative technique with a long history of use in the operating room and the office for the treatment of HPV-associated anal lesions. A recent publication showed no statistically significant differences between electrocautery and IRC in their efficacy and safety profile. In the ANCHOR study, clinicians may use electrocautery interchangeably with IRC. The choice of therapy typically depends on the prior training of the clinician and the technique with which they have the most experience. Non-surgeons in the U.S. who treat anal HSIL were primarily trained by [name] and his group to use IRC, but those with a surgical background may prefer electrocautery. The main advantages of electrocautery are that it is faster than IRC to perform and the electrocautery probe tip can be more precisely applied to the lesion than the IRC probe tip, which is larger in diameter. The main disadvantage of electrocautery is that it generates a smoke plume, requiring a smoke evacuator and mask protection from smoke for providers and patients in the room.

Other ablative treatments include use of surgical lasers. These modalities are less commonly used for anal HSIL, but patients treated with these techniques will be eligible for the HRQoL study.

Treatment under anesthesia (TUA) is a procedure performed by surgeons on patients who are given spinal or general anesthesia. It is typically performed in an operating room although some procedures may be performed in an office setting on patients with conscious sedation. Combined with post-procedural IRC, it has been shown to be effective in treatment of HSIL for patients with disease too widespread to treat with targeted ablation therapy⁹. TUA is usually required for only a small percentage of patients being treated for anal HSIL. These include 1) disease that is so extensive that it cannot be treated by any of the other methods described in this section, or 2) if a lesion is so large that it cannot be sufficiently biopsied in the office to establish or exclude a diagnosis of cancer to the satisfaction of the clinician. The disadvantage of TUA is that it is expensive compared with the other methods. In addition, TUA is only done when more extensive excision is required and patients typically experience more post-procedure side effects, including pain,

bleeding, and infection after TUA when compared with less aggressive treatment modalities.

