Topical agents. Topical 5% fluorouracil cream (5-FU) is typically used when disease is too extensive for IRC or electrocautery. It is given with the intent to clear as much of the lesion as possible, and while it is unusual for a large lesion to clear completely, it may be particularly useful to “debulk” a lesion to the point where it can then be treated with a targeted ablative approach such as IRC or electrocautery. Among 20 patients with extensive HSIL who were treated with topical 5-FU at UCSF by the PI’s team, complete response was seen in only 3 and no response was seen in one, but 16 had a significant decrease in volume of disease to 25-50% that allowed for in-office IRC. At UCSF, the protocol for use of topical 5-FU is for the patient to apply intra-anal or perianal 5-FU twice daily for 5 days, followed by a 9-day rest period. This cycle can be repeated eight times.

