Active monitoring or observation is the control arm of the ANCHOR study, and this approach is used clinically in a small percentage of cases. Given the diversity of treatments for anal HSIL, it is important that the participant sample recruited for the development of a symptom index measure include representatives of all the treatment modalities, including those not treated but actively monitored. It is expected that some participants will have been treated with multiple modalities; thus, these participants will be included in the HRQoL study as well.

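### Does coding only the most recent treatment for multi-modality participants undermine the check that all modalities are represented?

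*Protocol*

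**What the plan says.** Section 3.4 builds the referral identifier from a site number, one treatment letter (O, A, T or S) and a volume letter (L or H). The clinician box for the Information Sheet has one treatment field with those four letters. For participants with more than one modality the rule is: "If the patient has undergone multiple treatment modalities, the referral staff will select the most recently received treatment". The same section explains the purpose of the code: "It is important that the referral site indicate via the treatment code how each patient was treated". The stated reason is that patients may misreport their treatment. MSKCC staff must use this information to monitor sampling.

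Section 2.2 states the aim, that "it is important that the participant sample recruited for the development of a symptom index measure include representatives of all the treatment modalities". It adds: "It is expected that some participants will have been treated with multiple modalities". Those participants are to be included. Criterion 3.1.4 sets the window: "Participant must have received anal HSIL treatment in the last nine months", with a parallel nine-month diagnosis rule for observed participants.

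Section 7.1 lists the treatment modalities used (plural) among the health data. It then speaks of recording one modality per participant, so that sampling can be proportional to clinical practice, and of describing the sample by treatment modality. Section 5.0 plans no formal statistical analysis; interviews are coded by an expert panel.

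**The concern.** Section 2.2 itself describes two sequences that can end in ablation. Topical 5-FU may reduce a lesion "to the point where it can then be treated with a targeted ablative approach such as IRC or electrocautery". Of treatment under anesthesia it says: "Combined with post-procedural IRC, it has been shown to be effective in treatment of HSIL". When ablation comes last, both become an A, and the earlier T or S drops out of the code.

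Nothing else described in the protocol captures it systematically. Referring sites collect no data. The demographic sheet and language screener have no treatment item. The interview script mentions treatment where applicable but does not ask which treatments were received. Names, telephone numbers and recordings are destroyed soon after the interview.

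At stake would be the modality check in a sample of 20 to 40. Staff might judge topical or surgical experience absent or thin when people who had it were interviewed, and the published description would be incomplete.

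**Working it through.** The plan gives no figure for this point, so there is none to reproduce. The check has four steps.

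**1. Can two modalities fall inside the window?** Section 2.2 gives the 5-FU regimen as "twice daily for 5 days, followed by a 9-day rest period. This cycle can be repeated eight times".
- One cycle: 5 + 9 = 14 days.
- Eight cycles: 8 × 14 = 112 days. If eight repeats follow a first cycle: 9 × 14 = 126 days.
- Nine months: 9 × 365.25/12 = 273.9 days.
- Remainder: 273.9 − 112 = 161.9 days, or 273.9 − 126 = 147.9 days.

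A later ablation fits. This shows that the sequence is possible, not how often it occurs.

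**2. How many exposures could go unrecorded?** Inputs: N = 20 to 40 (Section 3.3.1) and m, the share of participants with exactly two modalities in the window. The protocol does not give m; the values below are assumptions. Recorded exposures = N. True exposures = N(1 + m). Unrecorded share = m/(1 + m).

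| m (assumed) | N = 20 | N = 40 | Unrecorded share |
|---|---|---|---|
| 10% | 2 of 22 | 4 of 44 | 0.1/1.1 = 9.1% |
| 20% | 4 of 24 | 8 of 48 | 0.2/1.2 = 16.7% |
| 30% | 6 of 26 | 12 of 52 | 0.3/1.3 = 23.1% |

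How many of these would be T or S cannot be derived. The reverse order (ablation first, then topical or surgery) is not ruled out and would hide an A. The 5-FU series in Section 2.2, where 16 of 20 patients became suitable for in-office IRC, does not help: it does not say how many then received IRC, and those patients were selected for extensive disease.

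**3. Which way can the code mislead?** A participant coded T had topical treatment, and one coded S had surgery. If all four letters occur among those interviewed, all four approaches are represented. The code can therefore confirm presence but cannot prove absence. The only possible mistake is to think a modality scarcer than it is, and the likely response would be to seek more such referrals. That does not harm the aim in Section 2.2.

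**4. What would a fuller code change?** Suppose sites circled every modality and flagged the latest. The flagged letter reproduces the present letter, so the sampling counts would be identical. Eligibility, the interviews and the panel coding would also be the same. Only a descriptive table would gain.

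The identifier, however, would change, because the circled letters form part of it. It now has 4 × 2 = 8 letter combinations. Assume that observation is never combined with a treatment. The flagged sets of A, T and S then number 3 single, 3 × 2 = 6 double and 3 triple, so 12; with O, 13; with volume, 13 × 2 = 26. That is a more distinctive treatment history in the identifier of at most 40 HIV-positive participants, in a study whose exemption rests on anonymity (Section 7.1).

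**The case for a change.** The strongest case for a change is that the protocol asks more of the code than one letter can give. Section 3.4 wants it to show how each patient was treated. Section 7.1 uses the plural for the data collected. Section 2.3 says that modality affects symptoms during and after treatment, so the treatments behind the interviews bear on content validity. Sites must already consult the treatment history to choose the latest modality, so circling the others needs no new source, and a flag would keep the exclusive counts.

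Some of this stands. The code is incomplete for participants whom the protocol expects, and the plural in Section 7.1 is looser than what the referral box delivers. Free-text notes may pick up earlier treatment, but not reliably.

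It does not carry the conclusion. Section 7.1 goes on to use the singular, both for recording each participant's treatment and for describing the sample, and one letter serves both. The questionnaire asks about the past 7 days, so the most recent treatment is a reasonable one to attach to the answers. Participants with several treatments still bring all of that experience to the interview; only their label is shorter. The change would also cost more than an instruction: it alters the identifier and needs IRB approval of an amendment at each participating institution (Section 7.2).

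**Conclusion.** No change follows. The rule is a stated and defensible convention, and the lost detail is a fair price for a short, exclusive code in an anonymous sample. On the assumed shares of 10% to 30%, the unrecorded exposures are 9% to 23%. That range rests wholly on the assumption, and neither the true share nor the net direction between modalities can be found in the protocol. Whatever the share, those interviewed, the interview content and the basis for judging content validity stay the same, provided staff read a missing letter as not shown to be present rather than as absent. An analyst would naturally label the sample description by most recently received modality, which is exactly what Section 3.4 defines.
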